## 11.1.2. Pre-Study Screening Phase

Potential subjects will be given complete information describing the study treatment and their role in the trial, and they will be encouraged to ask any questions regarding the trial. The risks and requirements of this clinical research trial will be explained to each potential subject. Those volunteering to take part will read and sign the Informed Consent Form for participation in the clinical research trial before any trial-related procedures are performed. Upon obtaining the signed informed consent, inclusion and exclusion criteria will be reviewed to verify the subject's eligibility.

During the screening visit, participants will undergo a clinical interview including a demographic questionnaire, documentation of medical history, physical examination, concomitant medications, Structured Clinical Interview for DSM Diagnosis (SCID), smoking history and habits and motivation to quit smoking.

#### 11.1.3. Baseline Phase

Eligible subjects will be assessed at Baseline for their self-report of cigarette consumption, confirmed by a quantitative assessment of urine cotinine levels (nicotine metabolite). Urine cotinine levels will be measured from a urine sample and sent to a core laboratory for analysis.

The following nicotine craving and nicotine dependence/withdrawal questionnaires will also be administered at baseline, in order to measure the subjects' baseline levels. Subjects will be requested to refrain from smoking for two hours before the baseline visit and before all treatment/assessment visits.

- 1) Nicotine Craving Scale (7 point VAS scale)
- Self-administered Fagerstrom Test of Nicotine Dependence (FTND) (Heatherton et al., 1991)
- 3) Minnesota Nicotine Withdrawal Scale (MNWS) (Hughes and Hatsukam 1986).
- 4) Self-administered Tobacco Craving Questionnaire (TCQ-SF) (Troop et al., 2003).

Cognitive test questionnaires, including MMSE and BSRT, will be reported at baseline.

Baseline data are defined as the data generated during the baseline visit prior to the first DTMS/sham treatment. Subjects who have completed all assessments at the baseline visit will be randomized to either the DTMS treatment group or the sham control group. The baseline visit should be performed within 7 days of the screening visit.

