#### 5.2. Secondary Objectives

- To compare the four-week continuous quit rate (CQR), representing abstinence during a consecutive 4 week period, between the two treatment groups. Weekly abstinence is defined as a subject's self-report (in diary) of no smoking (0 cigarettes/day during the whole week), confirmed by urine cotinine levels <200ng/ml. A missing confirmatory test will be considered negative, if the previous and the following weekly or 4 month follow-up confirmatory tests are negative. Quit rates are defined as the ratio of the number of patients meeting the quit criterion for at least 4 consecutive weeks to the total number of patients having assessments during a consecutive 4 week period.
- The secondary objective is to compare number of cigarettes smoked per day (per diary data) for all subjects.

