# 7.2. Subject Inclusion Criteria:

Subjects must fulfill the following criteria:

- Male or female subjects, 22-70 years old.
- Current, chronic (≥10 cigarettes/day) smokers, who smoke for more than 1 year, with no period of abstinence for greater than 3 months during the past year.
- Subjects who are motivated to quit smoking (with responses "very likely," or "somewhat likely" to the motivation questionnaire).
- Satisfactory answers on safety screening questionnaire for transcranial magnetic stimulation (Keel 2001).
- Gave informed consent for participation in the study.

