11.3.1. Abstinence and Continuous Quit Rates (CQR)

Abstinence is defined as a subject's self-report (section 11.3.1) of no smoking (0

cigarettes/day), confirmed by urine cotinine levels  $\leq$ 200ng/ml (section 11.3.2). The "cutoff" value of urine cotinine) is recognized as 200 ppm or 200ng/ml) for the determination of abstinence. Subjects with cotinine levels above this value will be considered to have not stopped smoking. Continuous Quit Rates (CQR) is defined as the ratio of the number of patients meeting the quit criterion (i.e., abstinence during a consecutive 4 week period) to the number of patients initially treated, will be assessed at Baseline, at the weekly visits during the treatment phase and at the 4 month follow-up visit.

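### Baseline cotinine is said to confirm smoking but no entry rule uses it, so for an entrant at or below 200 ng/ml the diary alone decides quitter status; separately, 11.3.1 misstates the cut-off unit 1000-fold

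*Protocol*

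**What the plan says.** - **Entry (Protocol 7.2, 7.3).** Smoking status is set by reported consumption: "Current, chronic (≥10 cigarettes/day) smokers, who smoke for more than 1 year". Neither list contains a cotinine value. Section 11.1.2 reviews eligibility at the screening visit.
- **Baseline (11.1.3).** Subjects already called eligible are assessed for "self-report of cigarette consumption, confirmed by a quantitative assessment of urine cotinine levels". The sample is "sent to a core laboratory for analysis". No cut-off is attached to the baseline result, no consequence follows from a low value, and nothing requires the result to be back first. The condition for randomisation is completion: "Subjects who have completed all assessments at the baseline visit will be randomized".
- **Primary endpoint (13.2.1).** An abstinent week is a diary with no cigarettes plus urine cotinine at or below 200 ng/ml. Four consecutive such weeks make a quitter. No fall from a positive baseline value is required.
- **Cut-off (11.3.1).** The value "is recognized as 200 ppm or 200ng/ml". The synopsis (primary objective), 5.1, 6, 11.3.1 and 13.2.1 use at or below 200 ng/ml. The secondary objective, in the synopsis and in 5.2, reads "confirmed by urine cotinine levels <200ng/ml".

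**The concern.** Biochemical confirmation is there so that the primary endpoint does not rest on self-report. It can do this only for a subject whose cotinine is above the cut-off while smoking. If the value is already at or below 200 ng/ml at entry and stays there, a true quit and an unreported continuation of smoking give the same laboratory result. The protocol claims a confirmation at baseline that its own procedures do not enforce. Such subjects can add successes to both arms that have nothing to do with treatment, which narrows the difference the trial is sized to detect.

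The unit error is a separate fault. It stands in the section that defines abstinence, and taken literally it would set a threshold that makes the biochemical check meaningless.

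**Working it through.** **1. Can a subject at or below the cut-off be randomised?**

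| Step | Section | Is a cotinine value required? |
|---|---|---|
| Eligibility review at screening | 11.1.2, 7.2, 7.3 | No |
| First cotinine sample | 11.1.3, 11.2.2 | Taken at baseline, sent to a core laboratory |
| Randomisation | 11.1.3 | No; assessments completed |
| Weekly abstinence | 13.2.1 | At or below 200 ng/ml, whatever the baseline value |

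Yes. For such a subject the weekly test is passed for as long as the value stays at or below the cut-off.

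**2. The plan's own sample size.** Inputs from 13.4, 13.5 and their subsections: sham 18%, active 38%, 80% power, two-sided 5%, one interim at about 65% information, nominal level 0.03154 at both looks, 82 per arm.

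With n per arm, the drift is θ = (pA − pS) / √{[pA(1 − pA) + pS(1 − pS)] / n}. Z1 has mean θ√0.65, Z2 has mean θ, both have variance 1, and their correlation is √0.65. Power = 1 − P(|Z1| < c and |Z2| < c), with c = 2.150 (two-sided 0.03154).

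- At θ = 0 the overall level is 0.0500, as planned.
- 80% power needs θ = 2.914. Then n = (0.38 × 0.62 + 0.18 × 0.82) × 2.914² / 0.20² = 0.3832 × 8.491 / 0.04 = 81.4, so 82 per arm and 164 in total. The stated figure is reproduced.
- At n = 82: standard error √(0.3832 / 82) = 0.0684, θ = 2.926, power 80.3%.

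**3. Effect of entrants at or below the cut-off.** The documents give no share, so this is an assumed range. Let f be the share of analysed subjects, equal in both arms, and q the proportion of them counted as quitters in either arm. Each rate becomes p(1 − f) + qf, and the difference becomes 20(1 − f) points.

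Example, f = 2%, q = 1: active 0.38 × 0.98 + 0.02 = 0.3924; sham 0.18 × 0.98 + 0.02 = 0.1964; difference 0.196; standard error √[(0.3924 × 0.6076 + 0.1964 × 0.8036) / 82] = 0.0695; θ = 2.820; power 77.3%.

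| f | Difference (points) | Power at 82 per arm, q = 0.5 | q = 1 | Total N for 80% |
|---|---|---|---|---|
| 0 | 20.0 | 80.3% | 80.3% | 164 |
| 1% | 19.8 | 79.3% | 78.8% | 168–170 |
| 2% | 19.6 | 78.2% | 77.3% | 172–176 |
| 5% | 19.0 | 74.9% | 72.8% | 186–196 |

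Of 164 analysed subjects, 1% to 2% is about 2 to 3 people (1.6 to 3.3).

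**4. Units.** In a fluid of about the density of water, 1 ppm = 1 µg/ml = 1000 ng/ml. So 200 ppm = 200,000 ng/ml, and 200 ng/ml = 0.2 ppm. The ratio is 1000.

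**The case against.** **The protocol has safeguards.** Section 12.2 withdraws subjects who do not comply with the entry criteria, and 13.8.1 limits the efficacy set to subjects who met them. An investigator could read a low baseline cotinine as contradicting the reported consumption. This does not close the gap: no entry criterion refers to cotinine, so a low value breaches none of them.

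**The harm may be small.** This largely stands. A false success needs a low value at entry, a value that stays low, and a false zero-cigarette diary for four consecutive weeks. A low-cotinine smoker who really quits is classified correctly, and one who records continued smoking fails. The pilot described in 2.4 reports that all self-reported abstinence was confirmed by cotinine; that is not evidence about baseline values, but it shows no sign of a problem. At the planned dropout, 270 × (1 − 0.37) = 170 subjects remain, which would absorb a 1% share.

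**Stronger readings that the text does not support.**
- *False quitters could make the device look effective.* Allocation is randomised and blinded, so such entrants are expected equally in both arms. They dilute the difference and do not bias the test towards success.
- *The ppm slip or the inequality is what lets the diary decide.* Neither does; only the missing entry rule has that effect. The ppm unit appears once, beside the ng/ml value, and every objective and endpoint that states a cut-off uses ng/ml. Nothing suggests results would be judged at 200,000 ng/ml.
- *The primary and secondary endpoints use different cut-offs.* The strict inequality may be an underline lost when the PDF was read; 13.1 likewise has >10 cigarettes a day where other sections have ≥10. Section 13.2.2 refers to the quit criterion without restating a cut-off. At most, a value of exactly 200 is affected.

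**Handling of low baseline values could be left to the SAP.** That is fair for an analysis rule. Who may be randomised is for the protocol to settle.

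**Conclusion.** The concern holds in a limited form. The protocol says baseline smoking is confirmed by cotinine, yet it neither requires a positive result nor makes randomisation wait for one. For an entrant who is, and stays, at or below 200 ng/ml, the biochemical part of the primary endpoint cannot discriminate.

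The consequence is non-differential dilution. Its size is unknown because the documents give no share of such entrants. The fall in power to about 77–79% at 1% to 2% is illustrative: it assumes equal shares in both arms, half or all of them counted as quitters, no treatment effect among them, and the planned two-look design at 0.03154. The heading of 13.5 says the interim was not performed, so the figures describe the design as planned and not the final test.

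The unit statement in 11.3.1 is wrong by a factor of 1000. That needs no assumption beyond urine having about the density of water.

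**What to change.** 1. **Entry rule.** Take the pre-treatment cotinine sample at the screening visit (11.1.3 places baseline within 7 days of it), and add to 7.2 a urine cotinine above 200 ng/ml, with the result available before randomisation. Cost: assays for subjects who then fail screening, and dependence on core-laboratory turnaround within the window.
2. **If that is not feasible,** because of turnaround or because enrolment is over (13.4 describes the dropout monitoring in the past tense), prespecify a sensitivity analysis of the primary comparison restricted to subjects with baseline cotinine above 200 ng/ml. The restriction uses a pre-treatment variable already collected, so the arms stay comparable. Cost: one extra analysis and the loss of the excluded subjects from it. The main analysis set does not change.
3. **Units.** In 11.3.1, delete the ppm figure and keep 200 ng/ml.
4. **Minor wording check.** Confirm against the source file that at or below 200 ng/ml is used throughout, including the secondary objective in the synopsis and 5.2. No cost beyond the edit.

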## 11.1.4. Treatment Phase

During the treatment phase subjects will receive daily prefrontal DTMS, 5 days per week for 3 consecutive weeks, followed by one weekly session for three weeks (for a total of 18 treatments over 6 weeks). Subjects will be asked to select a target quit date (TQD). The TQD will be scheduled within 7-14 days of the first treatment session, to allow for a minimum of 7 days of treatment before the quit attempt. Subjects will be instructed not to try to quit smoking prior to their TQD.

Subjects will be asked to refrain from smoking for two hours prior to the baseline visit and prior to all the treatment sessions. Prior to treatment stimulation onset, a smoking related cue/provocation will be presented to the subject. The smoking cue/provocation will consist of holding and handling a cigarette from the brand of cigarettes the subject is accustomed to smoke and viewing smoking related pictures for a period of 5 minutes. Immediately after the offset of the smoking cue/provocation presentation (while memory is reactivated) active or sham DTMS stimulation will be administered.

During the treatment phase, assessment visits will be performed weekly at weeks 2, 3, 4, 5 and 6 weeks from start of treatment. Assessment visits will be performed prior to the treatment session. Participants will be asked to keep a record of their smoking behavior on a diary card. At each of the weekly visits, smoking behavior will be evaluated, diary cards reviewed, information collected on changes in concomitant medications and adverse events, and urine cotinine levels monitored. Nicotine craving and nicotine dependence/withdrawal questionnaires will also be administered at each of the weekly visits. Subjects will be provided with a self-help educational booklet on smoking cessation ("Clearing the Air: How to Quit Smoking...and Quit for Keeps" National Cancer Institute 95-1647) and up to 10 minutes of brief counseling regarding smoking cessation will be provided at the end of each weekly visit in accordance with AHRQ Guidelines.

All procedures to be performed during the different visits are listed in the Time and Events Schedule in Attachment 1.

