### 13.2. Study Endpoints

# 13.2.1. Primary Efficacy Endpoint

The primary endpoint is the four-week continuous quit rate (CQR), representing abstinence during a consecutive 4 week period. Weekly abstinence is defined as a subject's self-report (in diary) of no smoking (0 cigarettes/day during the whole week), confirmed by urine cotinine levels  $\leq 200$  ng/ml. A missing confirmatory test will be considered negative, if the previous and the following weekly or 4 month follow-up confirmatory tests are negative. Quit rates are defined as the ratio of the number of patients meeting the quit criterion for at least 4 consecutive weeks to the number of patients initially treated and having at least one post-baseline assessment.

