#### 13.9.5. Efficacy analyses

• The continuous quit rate (CQR) at the 6 weeks visit will be compared between the study arms with a chi-squared test. In addition the CQR will be modeled with logistic regression; baseline daily number of cigarettes smoked, sex and center will be used as covariates.

Prognostic factors and sensitivity analysis for the CQR at the 6 week and/or 4 month follow-up visits will be performed in the following manner: adjustment for other covariates such as demographics or other baseline characteristics (e.g., sex, age, race and history of smoking) may be performed by adding these variables to the above described logistic model.

- Weekly point prevalence abstinence rates will be analyzed in the same manner.
- Daily number of cigarettes smoked will be presented over time and analyzed with a repeated measures analysis of covariance model. Baseline daily number of cigarettes smoked, sex and center will be used as covariates.

The analysis will be presented for all subjects in the analysis set and for the non-quitters only.

 Effect on withdrawal symptoms as measured by weekly scales measuring nicotine craving and dependence/withdrawal, including Fagerstrom Test for Nicotine Dependence (FTND), Minnesota Nicotine Withdrawal Scale SelfReport (MNWS), Tobacco Craving Questionnaire–Short Form (TCQ-SF) and Nicotine Craving Scale.

Fagerstrom Test for Nicotine Dependence scores will be presented in tabular form and compared between the treatment arms with chi-squared tests.

Minnesota Nicotine Withdrawal Scale Self-Report scores, Factor structure of Tobacco Craving Questionnaire–Short Form scores, and Nicotine craving scale scores will be presented over time and analyzed with a repeated measures analysis of covariance model. Baseline daily number of cigarettes smoked, sex and center will be used as covariates.

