# Appendix A: Time and Events Schedule

 Table 1: Screening and treatment period

		T	Week 1					Week 2					Week 3					Wk 4	Wk 5	Wk 6	4 MO
Visit	SC	BL	V1	V2	V3	V4	V5	V6	V7	V8	V9	V10	V11	V12	V13	V14	V15	V16	V17	V18	V19
TMS/Placebo						$\checkmark$									$\checkmark$					$\checkmark$	
Informed Consent a																					
Inclusion/ Exclusion	$\checkmark$																				
Medical history																					
Smoking history																					
Con Meds																		$\checkmark$	$\checkmark$		
Physical Examination																				$\checkmark$	$\checkmark$
Vital signs b , height & weight																				$\checkmark$	$\checkmark$
Randomization																					
Cotinine Sample																					
FTND																				$\checkmark$	
MNWS																		$\checkmark$	$\checkmark$	$\checkmark$	$\checkmark$
TCQ-SF																			$\checkmark$	$\checkmark$	$\checkmark$
Nicotine Craving Scale before smoking cue before treatment			$\checkmark$	$\checkmark$	$\checkmark$	$\checkmark$	$\checkmark$	$\checkmark$		$\checkmark$	$\checkmark$	$\checkmark$	$\checkmark$	$\checkmark$	$\checkmark$						
Nicotine Craving Scale after smoking cue before treatment			$\checkmark$	$\checkmark$	$\checkmark$	$\checkmark$	$\checkmark$	$\checkmark$		$\checkmark$	$\checkmark$	V			$\checkmark$	$\checkmark$	$\checkmark$	$\checkmark$			

Nicotine Craving Scale after treatment		$\checkmark$																		
Daily Smoking Diary	$\checkmark$																			
Auditory Test																			$\checkmark$	
Pregnancy Test c																				
MMSE																			$\checkmark$	
BSRT																				
Adverse Events d	$\checkmark$		$\checkmark$	$\checkmark$	$\checkmark$															

 a Informed consent has to be obtained prior to any study-related procedure.
 b Includes pulse and systolic and diastolic blood pressure. Both measurements will be done while the subject is sitting and after 5 minutes of rest.
 c For females of child-bearing potential.
 d Monitoring of adverse events begins after the Informed Consent Form is signed and the first study-related procedure is performed, and continues until the last study-related procedure is performed.

e all measures will take before rTMS treatment administration.

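### The quit-date window, the four-whole-week endpoint and the week-6 comparison leave no slack, and they conflict if the visit falls inside week 6 as the session schedule implies

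*Protocol*

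**What the plan says.** All references are to the protocol.

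- **Quit date.** Section 11.1.4: "The TQD will be scheduled within 7-14 days of the first treatment session". It adds: "Subjects will be instructed not to try to quit smoking prior to their TQD".
- **Sessions.** Section 11.1.4 gives daily sessions, five per week for three weeks, "followed by one weekly session for three weeks (for a total of 18 treatments over 6 weeks". Appendix A places V16, V17 and V18 in the columns for weeks 4, 5 and 6.
- **Assessment visits.** Section 11.1.4: "assessment visits will be performed weekly at weeks 2, 3, 4, 5 and 6 weeks from start of treatment". It then says: "Assessment visits will be performed prior to the treatment session". A footnote to Appendix A agrees: "all measures will take before rTMS treatment administration".
- **Endpoint.** Section 13.2.1 defines weekly abstinence as "no smoking (0 cigarettes/day during the whole week"), confirmed by urine cotinine, and success as meeting this for at least four consecutive weeks. It names no date by which the four weeks must end.
- **Analysis.** Section 13.9.5: "The continuous quit rate (CQR) at the 6 weeks visit will be compared between the study arms with a chi-squared test". Section 13.9.7 (Pooling) also uses quit status at week 6.
- **After week 6.** Section 11.1.5 schedules one further visit, at 4 months from screening, and only for participants who had quit. Section 11.3.1 lists the 4-month visit among the times at which the quit rate is assessed.

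**The concern.** Abstinence is not meant to begin before day 7 and may begin as late as day 14. Four whole weeks take 28 days. A reading at week 6 has to accommodate both, and whether it does depends on which day the week-6 visit is held. The text points to two different days and states no visit window.

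What is at stake is who counts as a primary success. If the visit falls inside week 6, a subject who follows the quit-date instruction and never smokes again can be recorded as a failure only because of the quit date chosen and the day of the visit. Both observed quit rates then fall, the difference between the arms shrinks with them, and power is lost.

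**Working it through.** **Inputs.** Quit day d = 7 to 14 (section 11.1.4). Required run: 4 weeks × 7 = 28 days (section 13.2.1). Primary reading at the 6-week visit, day v (section 13.9.5). Convention: first session = day 0, the quit day is the first smoke-free day, and the visit precedes that day's session.

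**The plan's own figures.** 5 × 3 + 3 = 18 sessions, as stated. Six weeks from day 0 cover days 0-41, and week 6 is days 35-41. The sample size also reproduces: two looks at 65% and 100% information, each at two-sided 0.03154 (overall alpha 0.0500), 80% power, 18% versus 38% and unpooled variance give 81.4, hence 82 per arm and 164 in total.

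**Smoke-free days available.** Complete smoke-free days before the visit = v − d. The subject can qualify only if v − d ≥ 28, so the latest quit day that qualifies is v − 28.

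| Visit day v | Latest quit day that qualifies | Quit days that qualify (of 8) | Share that misses if quit days are uniform (assumption) |
|---|---|---|---|
| 35 | 7 | 1 | 7/8 = 87.5% |
| 36 | 8 | 2 | 75% |
| 37 | 9 | 3 | 62.5% |
| 38 | 10 | 4 | 50% |
| 39 | 11 | 5 | 37.5% |
| 40 | 12 | 6 | 25% |
| 41 | 13 | 7 | 12.5% |
| 42 | 14 | 8 | 0% |

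**Reading A: session schedule, v = 35 to 41.** For d = 14, v − d runs from 35 − 14 = 21 to 41 − 14 = 27, always short of 28. For d = 13, only v = 41 reaches 28. For v = 35, only d = 7 does.

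**Reading B: elapsed time, v = 42.** For d = 14, 42 − 14 = 28 (days 14-41). The whole window fits. A visit one day early, or a cigarette on the quit date itself, breaks it for d = 14.

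**Effect on power (illustration).** Let f be the fraction of true four-week quitters, equal in both arms, who cannot qualify. The rates become p₁ = 0.18(1 − f) and p₂ = 0.38(1 − f), with Δ = p₂ − p₁ and p̄ their mean. For a single look with n = 82 per arm:

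power = Φ{[Δ√n − z√(2p̄(1 − p̄))] / √(p₁(1 − p₁) + p₂(1 − p₂))}

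For f = 0.25 at two-sided 0.05, p₁ = 0.135, p₂ = 0.285, Δ = 0.15 and p̄ = 0.21. This gives (0.15 × 9.055 − 1.960 × 0.576) / 0.566 = 0.405, and Φ(0.405) = 66%.

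| f | Power at 0.05 | Power at 0.03154 |
|---|---|---|
| 0 | 82% | 76% |
| 0.10 | 76% | 70% |
| 0.25 | 66% | 58% |
| 0.50 | 45% | 38% |

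The documents do not give f, so these rows show sensitivity and are not an estimate.

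**The case against.** The strongest reply is that section 11.1.4 counts the visits from the start of treatment. Read as elapsed time, the visits fall on days 14, 21, 28, 35 and 42. The first is the last allowed quit date, and the four that follow confirm exactly four weeks. This stands, and it rules out a stronger conclusion that a reader might draw: that a late quitter can never meet the endpoint. It does not settle the matter. Day 42 lies outside the six weeks that hold the 18 sessions, whereas the assessment is supposed to precede a session and Appendix A puts V18 in week 6.

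Second, the endpoint definition sets no end date, its missing-test rule accepts the 4-month cotinine, and section 11.3.1 assesses the quit rate at 4 months as well. So the week-6 limit comes from the analysis text, not from the definition. That is true, but the rescue is uncertain. No weekly cotinine visit is described between week 6 and month 4, only those who had quit return, and the missing-test rule deals with missing tests, not with a week that has not yet elapsed.

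Third, visit windows and the mapping of diary days to weeks are commonly left to the SAP, which is not at hand. That holds for the counting rule. It does not hold for a reading that the visit schedule may never collect.

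Fourth, a reader might infer that 38% to 88% of perfect abstainers would be lost. That range needs a Monday start, weekday visits (days 35-39) and uniform quit dates, none of which the protocol states.

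**Conclusion.** The point holds as an unreconciled visit date with no slack. On the protocol's own session schedule, a continuously abstinent subject who quits on day 14 is scored a failure on every possible visit day, and earlier quit dates fail too, depending on the day. On the elapsed-time reading, all allowed quit dates fit, the last one exactly. Two readings of one section therefore give the same subject different primary outcomes.

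The size cannot be set from the document. With uniform quit dates as an assumption, the share of perfect abstainers who miss runs from 0% (day 42) to 88% (day 35). A reader might also suspect bias towards one arm. The document does not support this: the quit-date rule and the visit schedule are the same in both blinded, randomised arms. The expected cost is lower quit rates and lower power.

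**What to change.** Reconcile sections 11.1.4, 13.2.1, 13.9.5 and 13.9.7 and Appendix A, on the measurement side only:

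- State that the final primary diary and cotinine reading is taken no earlier than day 42, or no earlier than 28 full days after the subject's quit date.
- Count the four weeks as 28 consecutive diary days, not by visit label.
- State whether the qualifying run may end after week 6.

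The cost is modest. For some late quitters the reading may be separated from the last session, which could mean one rescheduled or additional urine sample.

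If the visits are already complete, fix the counting rule before unblinding and report how many subjects had their last reading before quit date + 28 days. Treatment sessions and the quit-date instruction are not addressed here.
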